### **2.5.3 Windows for time points**

This D1 selection visit must be conducted within 3 months (6 months for US) after completion of the Extension Study CAMMS03409. When possible, the visit will be performed at the same time as the last visit of the Extension Study CAMMS03409. For the follow-up visits, the protocol specified time window is  $\pm 14$  days of target dates for the post-baseline scheduled visits. The target dates for the scheduled visits are based on the calendar date of the D1 selection. All scheduled visits including those that occurred outside the specified windows will be included in the efficacy analysis.

#### **2.5.3.1 Algorithm for Determining Analysis Visit Windows for Safety Observations**

For the safety assessment, the reference date for the derivation of relative days of events or findings will be corresponding to TOPAZ baseline definition specified in [Section 2.4.5](#).

Selected safety variables will be summarized by the following analysis window:

- CBC with differential (including platelet count), Serum Creatinine, liver function and Urinalysis (assessed monthly for all the patients re-treated with alemtuzumab and for 48 months after last infusion)
- TSH (assessed every 3 months for all the patients re-treated with alemtuzumab and for 48 months after last infusion)
- Vital signs variable (assessed every 6 months from TOPAZ Day 1 to TOPAZ Month 60, at End of Study (EOS) visit, and at unscheduled visits.)

If a patient withdraws after the date of first study treatment, but prior to the first scheduled visit, data from the early withdrawal visit will be assigned to the analysis visit corresponding to the first scheduled visit. For all other visits, the lower bound and the upper bound for the analysis visit windows are defined as the midpoints of the target date of scheduled visits. If the date of the early withdrawal or an unscheduled visit falls in between the lower bound and the upper bound for a scheduled visit, then it will be assigned to that visit. For example, for the vital sign data, the lower and upper bound for the Month 18 analysis visit in a 6 month visit schedule will be Month 15 and Month 21 respectively, i.e. Month  $18 \pm 3$  months. If the early withdrawal visit date for the vital

sign assessment falls at Month 20 (i.e., between Month 15 and Month 21), then this early withdrawal visit will be assigned to the Month 18 analysis visit.

If only one record is within an analysis visit window, the data from that record will be used in the summary statistics and by visit analyses. If more than one record is within the same analysis visit window, the record from the regularly scheduled visit will be used in the summary statistics and by visit analyses. If more than one record is from a regularly scheduled visit, or more than one record is from unscheduled visits within the same analysis visit window, the record from the visit nearest to the middle of the interval will be used in the summary statistics and by visit analyses. If two visits are “tied” before and after the middle of the interval, the later record will be used in the summary statistics and by visit analyses. If the scheduled visit does not have any record but the windowed unscheduled visit is in an analysis visit window, data from the unscheduled visit will be used for the summary statistics and by visit analyses.

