## 2 STATISTICAL AND ANALYTICAL PROCEDURES

### 2.1 ANALYSIS ENDPOINTS

#### 2.1.1 Demographic and baseline characteristics

The TOPAZ baseline value is defined as the available value assessed on or prior to the V01 Selection visit, unless otherwise specified. The last available value in previous studies can be considered as the baseline if they were evaluated within the pre-specified time window. For brain imaging result, if the last non-missing assessment performed within 6 months prior to the V01 selection visit, it can be considered as baseline. For vital sign, physical examination, EDSS and questionnaires, the time window is 3 months.

For efficacy endpoints (EDSS, MRI), the baseline from prior studies will be considered as long-term baseline, which is defined as last available assessment prior to first dose of alemtuzumab or SC IFNB-1a administration.

All baseline safety and efficacy parameters (apart from those listed below) are presented along with the on-treatment summary statistics in the safety and efficacy sections ([Section 2.4.5](#) and [Section 2.4.4](#)).

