#### **2.3.1.2 48 months follow-up population**

The population is defined as all safety patients who have received study drug in CAMMS223, CAMMS323, CAMMS324 or CAMMS03409, that didn't complete 48 months of follow-up at the screening visit in TOPAZ study.

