#### **General common rules**

All safety analyses will be performed on the safety population as defined in [Section 2.3.1.1](#), unless otherwise specified, using the following common rules:

- The baseline value is defined as the available value assessed on or prior to the V01 Selection visit, unless otherwise specified. If laboratory, vital sign and physical examinations were performed in CAMMS03409 study within the pre-specified time-windows, then the last assessment within the time-window can be considered as baseline when the corresponding V01 assessments are missing.
- The potentially clinically significant abnormality (PCSA) values are defined as abnormal values considered medically important by the Sponsor according to predefined criteria/thresholds based on literature review and defined by the Sponsor for clinical laboratory tests and vital signs (PCSA version dated May 2014 [[Appendix A](#)])
- PCSA criteria will determine which patients had at least 1 PCSA during the treatment-emergent adverse event period, taking into account all evaluations performed during the treatment-emergent adverse event period, including nonscheduled or repeated evaluations.

The number of all such patients will be the numerator for the on-treatment PCSA percentage

- The treatment-emergent PCSA denominator by group for a given parameter will be based on the number of patients assessed for that given parameter in the treatment-emergent adverse event period in overall group and by subgroups (IAT vs DAT) on the safety population.
- For quantitative safety parameters based on central laboratory/reading measurements, descriptive statistics will be used to summarize results and change from baseline values by visit and analysis group.
- The analysis of the safety variables will be essentially descriptive and no systematic testing is planned.

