#### **2.4.5.3 Analyses of laboratory variables**

Laboratory analysis will be conducted for retreated population and 48 months follow-up population. The baselines for each population are defined as below.

- Retreated population baseline: The last non-missing assessment prior to first dose of alemtuzumab in TOPAZ study. The baseline should be taken within 2 weeks prior to the treatment for laboratory assessment except for HPV and pregnancy test. For HPV and pregnancy test, it can be taken in 12 months before the treatment.
- 48 months follow-up population baseline: The last non-missing assessment prior to the last dose of alemtuzumab in previous studies. The baseline should be taken within 2 weeks

prior to the treatment for laboratory assessment except for HPV and pregnancy test. For HPV and pregnancy test, it can be taken in 12 months before the treatment.

The summary statistics (including number, mean, median, Q1, Q3, standard deviation, minimum and maximum) of all laboratory variables (central laboratory values and changes from baseline) will be calculated for each visit or study assessment (baseline, each postbaseline time point, last on-treatment and/or worst on-treatment value and/or other specific assessment) in overall group and by subgroups (IAT vs DAT). This section will be organized by biological function [Section 2.1.4.3](#).

The incidence of PCSAs (list provided in [Appendix A](#)) at any time during the treatment-emergent adverse event period will be summarized by biological function and in overall group and by subgroups (IAT vs DAT) whatever the baseline level and/or according to the following baseline status categories:

- Normal/missing
- Abnormal according to PCSA criterion or criteria

For parameters for which no PCSA criteria are defined, similar table(s) using the normal range will be provided.

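### SAP 2.5.3.1 leaves the time origin for laboratory windows in conflict between selection visit and infusion, and no rule censors 48-month follow-up laboratory data at retreatment

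*SAP*

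**What the plan says.** **Reference date.** SAP 2.5.3.1 uses one rule for all safety variables: "the reference date for the derivation of relative days of events or findings will be corresponding to TOPAZ baseline definition specified in" Section 2.4.5. Window bounds are the midpoints between scheduled-visit target dates. SAP 2.5.3 gives the only definition of those dates: "The target dates for the scheduled visits are based on the calendar date of the D1 selection".

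**Baseline.** SAP 2.1.1 states: "The TOPAZ baseline value is defined as the available value assessed on or prior to the V01 Selection visit, unless otherwise specified". The common rules in 2.4.5 repeat this: "The baseline value is defined as the available value assessed on or prior to the V01 Selection visit, unless otherwise specified".

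**Laboratory data.** SAP 2.4.5.3 limits laboratory analysis to the retreated and the 48-month follow-up populations and gives each its own baseline. For retreated patients it is "The last non-missing assessment prior to first dose of alemtuzumab in TOPAZ study". For the follow-up population it is the last value before the final dose in the previous studies. By-visit summaries of values and changes from baseline are planned.

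**Sampling.** SAP 2.1.4.3 and Protocol 10.1.6.2 schedule blood counts, creatinine, liver tests and urinalysis monthly, and TSH every 3 months, until 48 months after the last infusion. Protocol 8.1.1 sets no fixed time for retreatment.

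**Membership.** SAP 2.3.1.2 defines the follow-up population as patients previously given study drug "that didn't complete 48 months of follow-up at the screening visit in TOPAZ study". No rule ends membership, or a patient's data, at retreatment.

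**The concern.** The laboratory question is how counts, creatinine, liver tests and TSH behave after an infusion. If windows are counted from D1, a visit label says little about time since treatment. A patient retreated at TOPAZ Month 30 would have the first monthly post-infusion sample filed under Month 31, next to samples from patients at quite different distances from their infusion.

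The change from baseline would still be measured from the pre-infusion value, so the window and the change would have different origins. In the retreated population, samples taken in TOPAZ before retreatment would fall in positive visit windows although they precede their own baseline.

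The second issue does not depend on the clock. A patient can belong to both laboratory populations. After retreatment, the same value enters both sets of summaries, once against the pre-retreatment baseline and once against the baseline before the earlier course. Safety is the primary endpoint (SAP 2.1.4), so the origin should not be left to the programmer.

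**Working it through.** **1. The plan's own figure.** The SAP's example is the Month 18 vital-sign window in a 6-month schedule. By the midpoint rule, (12 + 18)/2 = 15 and (18 + 24)/2 = 21, that is Month 15 to Month 21, as stated. The same rule gives ±0.5 month for monthly tests (Month 12 = 11.5 to 12.5) and ±1.5 months for TSH (10.5 to 13.5). The widths are clear; the origin is not.

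**2. Which origin?**
- *Pointing to D1:* the term TOPAZ baseline is defined at V01 in 2.1.1; the general rule in 2.4.5 uses V01; the only target dates in the SAP run from D1.
- *Pointing to the infusion:* both V01 definitions allow exceptions; 2.4.5.3, inside the cross-referenced section, makes one for laboratory data; the laboratory bullets in 2.5.3.1 refer to the last infusion, while the vital-sign bullet refers to TOPAZ Day 1; 2.5.3.2 names D1 outright for efficacy and 2.5.3.1 does not.

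Two programmers could build different tables from this text. Even one who chose the infusion would find no infusion-based target dates in the SAP.

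**3. Consequence if D1 is the origin.** Let m be the TOPAZ month, t0 the months from last prior infusion to D1 (0 to <48), and r the TOPAZ month of first retreatment. Time since infusion is m + t0 in the follow-up population (scheduled sampling stops at 48) and m − r in retreated patients.

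The ranges need no distributional assumption. The other entries do, because the documents give no infusion timing. They assume t0 uniform on 0–48, and r uniform on 0–48 or on 0–60. Among patients already infused by month m ≤ 48, time since infusion is then uniform on 0 to m under either choice, with SD m/√12.

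| D1 window | Follow-up: months since infusion | Share still sampled | IQR | Retreated, already infused: range | SD | Within 3 months | Not yet retreated (0–48 / 0–60) |
|---|---|---|---|---|---|---|---|
| Month 12 | 12–48 | 36/48 = 75% | 21–39 | 0–12 | 12/√12 = 3.5 | 3/12 = 25% | 75% / 80% |
| Month 24 | 24–48 | 24/48 = 50% | 30–42 | 0–24 | 24/√12 = 6.9 | 3/24 = 12.5% | 50% / 60% |

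Patients not yet retreated have scheduled samples only while within 48 months of an earlier infusion, so the last column is not a share of the values in the table.

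**4. Consequence if the 2.4.5.3 baselines are the origin.** Each window spans one month (three for TSH) of time since infusion. The mixing does not arise for a patient's first TOPAZ course.

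**5. Overlap, under either origin.** On the earlier course's clock, sampling runs to TOPAZ month 48 − t0. If retreatment comes first, the doubly counted span is 48 − t0 − r months. The protocol requires at least 12 months between courses, so t0 + r ≥ 12 and the span is at most 48 − 12 = 36 months. It could be longer if the analysis is not cut at 48 months after the earlier course, and the SAP states no such cut. SAP Appendix A includes potentially clinically significant abnormality (PCSA) criteria that depend on baseline: creatinine change of at least 30% or 100%, and hemoglobin decrease of at least 20 g/L. For these, the choice of baseline can change whether a post-retreatment value counts.

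**The case against.** The strongest defence is that the SAP already provides infusion-based laboratory baselines. SAP 2.4.5.3 sits in the section that 2.5.3.1 cites, and the V01 definitions yield where something else is specified. The D1 target dates carry a ±14-day window for site visits, whereas laboratory draws are monthly ±3 days from the infusion. The D1 reading also puts samples in post-baseline windows ahead of their own baseline, which makes it the less coherent one. This stands. A reader might infer that laboratory windows are definitely counted from the selection visit; the documents do not support that. They conflict.

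It is also fair that the analyses are descriptive, with no systematic testing. Threshold-based PCSA incidence at any time, the listing of possible Hy's law cases and the tables of adverse events of special interest do not use the windows. A reader might infer that a post-infusion signal would be lost, or that a peak in the first 3 months would shrink to one eighth. The first does not follow, because those outputs remain. The second needs the D1 reading, uniform retreatment timing and an effect confined to 3 months, none of which the documents state.

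The laboratory bullets in 2.5.3.1 mention only retreated patients. Since 2.1.4.3 gives a schedule for both groups, this is loose wording, not an exclusion.

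On the overlap, being in two descriptive populations is not causal attribution to two courses. But no section supplies a censoring rule, so the point about the wrong baseline remains.

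**Conclusion.** The concern holds in two parts.

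First, the reference date for laboratory windows is in conflict: D1 on the plain reading, ambiguous at best. If D1 is used, by-visit tables mix times since infusion (12 to 48 months in the follow-up population's Month 12 window), and windows and changes from baseline have different origins. If the 2.4.5.3 baselines are used, this does not arise for a first TOPAZ course. The 6.9-month SD, 12.5% and 50% at Month 24 are illustrations only. They assume the D1 reading and retreatment uniform over Months 0–48; with 0–60 the 50% becomes 60%.

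Second, whichever origin is meant, post-retreatment values stay in the 48-month follow-up population and are compared with a baseline before the earlier course, for up to 36 months on that course's 48-month clock. The number of patients affected cannot be derived from the documents.

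The effect is on descriptive laboratory summaries and baseline-dependent PCSAs. Without censoring, an any-time threshold count in the follow-up population can also include a post-retreatment value, although the windows play no part in that. The SAP should be corrected before the tables are programmed; the point does not undermine the safety evaluation as a whole.

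**What to change.** In SAP 2.5.3.1:
- Set laboratory Day 0 to match the 2.4.5.3 baselines: first TOPAZ infusion for the retreated population, last prior-study infusion for the 48-month follow-up population.
- Define monthly windows, and 3-monthly windows for TSH, from that date, and name both populations in the laboratory bullets.
- State how later TOPAZ courses are handled. One option keeps the first-dose baseline and Day 0 for the main table and adds a table by time since the most recent course. Resetting Day 0 at each course in the main table would not match the single baseline in 2.4.5.3.
- Keep the D1 clock for scheduled-visit vital signs.

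In SAP 2.3.1.2 or 2.4.5.3, end the follow-up population's laboratory data at the first TOPAZ infusion.

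The cost is SAP wording and programming. The dates are already collected, and no new assessments are needed.

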#### 10.1.4 End of study (EOS) visit

This visit will be performed in one of the following situations:

- At the end of the study. This visit corresponds to the Visit M60 $\pm$ 14D.
- At the end of the study period of 5 years, for all the ongoing patients, the next scheduled site visit will be changed into an EOS visit.
- If the patient is prematurely withdrawn from the study.

The following items will be checked/performed and recorded:

- Safety assessments ([Section 9.5](#)).
  - AE collection.
  - Vital signs and physical examination.
- Efficacy assessments ([Section 9.6](#)).
  - MS relapse verification.
  - EDSS.
  - Brain imaging to include: G-MRI, MRI-T1 and MRI-T2 T1 pre- and post-Gadolinium (Gd), T2/PD, FLAIR and T1 sagittal sequences (only if not performed in the previous 6 months).
  - Health questionnaires: SF-36, FAMS and EQ-5D.
- Pharmaco-economic assessment: modified HRUQ/HRPQ ([Section 9.7](#)).
- Concomitant medication.
- Blood sample collection for pharmacogenomic analysis (for consenting patients only).  
Omit if already collected during a prior study visit.

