### **2.5.3.2 Algorithm for Determining Analysis Visit Windows for Efficacy Observations**

For the efficacy assessment, the reference date for the derivation of relative days of events or findings will be D1 selection visit.

Selected efficacy variables will be summarized by the following analysis window:

- EDSS (assessed every 6 months from TOPAZ Day 1 to TOPAZ Month 60, at End of Study (EOS) visit, and at unscheduled visits.)
- SF-36, FAMS and EQ-5D (assessed yearly from TOPAZ Day 1 to TOPAZ Month 60, and at End of Study (EOS) visit.)
- MRI assessments (assessed yearly from TOPAZ Day 1 to TOPAZ Month 60, and at End of Study (EOS) visit.)

The algorithm for determining analysis visit windows and the observations to be used in the safety analyses will be applied to the above efficacy assessments in a similar manner. For efficacy analyses, all visits up to the end of the study, including those outside the protocol specified windows will be included.

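### An end-of-study visit at M42 or M54 falls on a bound of the yearly analysis windows, so the final quality-of-life record is dropped or mislabelled by about six months; MRI is affected less, mainly by mislabelling

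*SAP*

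**What the plan says.** **When EOS happens.** The study runs five years from the first enrolment (Protocol 6.2). After that, "for all the ongoing patients, the next scheduled site visit will be changed into an EOS visit" (Protocol 10.1.4). Scheduled visits are six-monthly and include M42 and M54, each ±14 days (Protocol 10.1.2).

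**What is collected.** SF-36, FAMS and EQ-5D are collected at every EOS visit (Protocol 9.6.4 to 9.6.6 and 10.1.4). MRI is repeated at EOS only if there was no scan in the preceding six months (Protocol 9.6.3; SAP 2.1.3.3).

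**How records are assigned.** In SAP 2.5.3.1, "the lower bound and the upper bound for the analysis visit windows are defined as the midpoints of the target date of scheduled visits". The example given is that "the lower and upper bound for the Month 18 analysis visit in a 6 month visit schedule will be Month 15 and Month 21". An early-withdrawal or unscheduled date that "falls in between the lower bound and the upper bound for a scheduled visit, then it will be assigned to that visit".

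**Competing records.** "If more than one record is within the same analysis visit window, the record from the regularly scheduled visit will be used". If several are scheduled, or several are unscheduled, the one nearest the middle of the window is taken.

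**Extension to efficacy.** SAP 2.5.3.2 says that the algorithm "will be applied to the above efficacy assessments in a similar manner". The list includes "SF-36, FAMS and EQ-5D (assessed yearly from TOPAZ Day 1 to TOPAZ Month 60, and at End of Study (EOS) visit") and "MRI assessments (assessed yearly from TOPAZ Day 1 to TOPAZ Month 60, and at End of Study (EOS) visit"). The same section adds that efficacy analyses include all visits up to study end, including those outside the protocol windows.

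**The concern.** A midpoint rule works when visits cluster around the targets. Here, a planned visit with mandatory quality-of-life collection sits midway between two targets. A few days then decide whether the patient's final record disappears from the by-visit tables or appears under the wrong year.

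Protocol 9.2 promises efficacy, including quality of life, from baseline through the last study visit. SAP 2.4.4.1.5 calculates percent change in lesion volume and brain parenchymal fraction from one year to the next, so an M54 scan labelled M60 would show about six months of change as a year's change. Patients who withdraw soon after an annual visit can lose their exit quality-of-life record in the same way.

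**Working it through.** **1. The SAP's own example.** Midpoints on the six-month grid: (12 + 18)/2 = 15 and (18 + 24)/2 = 21. This reproduces the M15 to M21 window for Month 18.

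**2. The same rule on the yearly grid.**

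| Annual visit | Lower bound | Upper bound |
|---|---|---|
| M36 | (24 + 36)/2 = 30 | (36 + 48)/2 = 42 |
| M48 | (36 + 48)/2 = 42 | (48 + 60)/2 = 54 |
| M60 | (48 + 60)/2 = 54 | none defined (no later target) |

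M42 and M54 are the bounds themselves, 6.0 months from each neighbouring annual target.

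**3. Who has EOS there.** EOS month = smallest multiple of 6 at or above (60 − enrolment lag), with lag in months after the first patient.

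| Lag | EOS |
|---|---|
| 0 to <6 | M60 |
| 6 to <12 | M54 (bound) |
| 12 to <18 | M48 |
| 18 to <24 | M42 (bound) |

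Accrual length is not stated. With uniform accrual over A months (assumption), the share of completers with a half-year EOS is: A = 6, 0; A = 9, 3/9 = 33%; A = 12, 6/12 = 50%; A = 15, 6/15 = 40%; A = 18, 6/18 = 33%; A = 24, 12/24 = 50%.

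**4. Quality of life.** Assume visit dates uniform over the 29 days from −14 to +14 around target, independently between visits.
- Before the bound: 14/29 = 48%. The record shares a window with the M36 or M48 record. If EOS is not a regularly scheduled visit, the annual record wins for being scheduled. If it is, the annual record wins for being nearer the middle (about 0 against about 6 months). If the annual record is missing, the EOS record is used and labelled about six months early.
- On the bound: 1/29 = 3.4%. No owner is stated.
- After the bound: 14/29 = 48%. It is the only record in the window and is labelled M48 or M60, about six months late.

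As a share of all completers with an annual record present, dropped records are 33% × 48% = 16% up to 50% × 48% = 24%, for accrual of 9 to 24 months. The share labelled late is the same.

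**5. MRI.** Under the same assumption a scan is due when EOS is more than six months after the annual scan, that is, when the EOS deviation exceeds the annual-visit deviation. There are 29 × 28/2 = 406 such pairs out of 29² = 841, or 48%. Of the 406:
- Before the bound: 14 × 13/2 = 91, or 22%.
- On the bound: 14, or 3.4%.
- After the bound: 406 − 91 − 14 = 301, or 74%.

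Among half-year EOS patients, 91/841 = 11% would have a scan dropped from by-visit summaries and 301/841 = 36% a scan labelled late. The other 52% have no EOS scan. When both visits are exactly on target the interval is 6.0 months, so whether a scan is due is itself unclear.

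**6. Early withdrawal.** Quality of life taken within six months after an annual visit lies in that visit's window and loses to its record, if there is one. An exception is withdrawal before the first scheduled visit, which SAP 2.5.3.1 assigns to that visit. A withdrawal less than six months after an annual scan requires no new scan.

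**7. EDSS.** On its six-month grid, M42 has window 39 to 45 and M54 has 51 to 57. There is no border problem.

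**The case against.** **The yearly windows are inferred.** The SAP prints only a six-month example, and M42 and M54 are scheduled visits. But the example is tied to its own visit schedule and SAP 2.5.3.2 describes MRI and quality of life as yearly, so a 12-month grid is the natural reading. The assignment sentence names only early-withdrawal and unscheduled visits, which leaves an EOS that replaces a scheduled visit without its own rule.

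**All visits are to be included.** SAP 2.5.3.2 says so and names EOS separately. It defines no EOS analysis window, however, and the inclusion statement does not override the one-record rule for summaries and by-visit analyses.

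**MRI is not like quality of life.** This stands. A reader might infer that half of final scans are lost. The scan is conditional, and the figure is about 11% of half-year EOS patients.

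**The cumulative lesion count.** A reader might infer that a scan dropped from a window is also missing from the cumulative total. The documents do not support this: SAP 2.1.3.3.1 sums counts through the end of study, and the one-record rule is limited to summary statistics and by-visit analyses. Confirmation is enough.

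**The effect is small.** This stands in part. These are secondary endpoints, and the quality-of-life analysis is descriptive with an optional supportive model (SAP 2.4.6). The long-term baseline lies at least 2 + 4 = 6 years before TOPAZ entry (SAP 1.4). At M54 a six-month shift is therefore at most 0.5/10.5 = 4.8% of the elapsed time. That answer does not cover year-to-year MRI change, where six months is half the labelled interval, or records that are dropped.

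**Conclusion.** The point holds for the yearly measures. For quality of life, the stated rules drop about 48% of half-year EOS records from by-visit summaries (or label them six months early if the annual record is missing) and label about 48% six months late. The remaining 3.4% have no defined window. For MRI the problem is smaller and is mainly mislabelling. These figures rest on independent uniform ±14-day visit dates.

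A reader might infer that many completers are affected. The documents do not settle that: the range is 0% at 6 months of accrual and 33–50% at 9 to 24 months, assuming uniform accrual. A March 2016 US amendment to an April 2014 protocol widened the entry window so that more patients could enrol. This suggests accrual longer than six months but does not prove it.

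EDSS, relapse endpoints and the primary safety objective are not affected. The change is worth making because it is cheap, but no main conclusion of the study depends on it.

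**What to change.** In SAP 2.5.3.2, for SF-36, FAMS, EQ-5D and MRI:

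- State which window owns a date that falls on a bound.
- Do not map an EOS or withdrawal record from a half-year visit to an annual visit. Report it in a separate EOS/last-observed row with its actual time since baseline.
- Confirm that EOS scans count in the cumulative lesion total of SAP 2.1.3.3.1.

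Do not add six-monthly visit levels to the models for these measures. Such levels would be sparse and filled mainly by later enrollees and patients who withdrew.

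The cost is SAP wording, one additional table row and one derivation. No new data are needed and no protocol change is required.
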